5.1.3.1 Prior therapies date imputation

See Section 5.1.3.

5.1.3.2 Post therapies date imputation

See Section 5.1.3.

5.1.3.3 Other imputations

None

5.2 AEs coding/grading

Not applicable

5.3 Laboratory parameters derivations

Not applicable

5.4 Statistical models

Not applicable

5.4.1 Analysis supporting primary objective(s)

Not applicable

5.4.2 Analysis supporting secondary objective(s)

Not applicable

5.5 Rule of exclusion criteria of analysis sets

PDs excluded from the ENR or SAF are shown in Table 5-1. Patients with only PDs that are not included in the list will not be excluded from any analysis sets.

Table 5-1 Protocol deviation criteria leading to exclusion from the analysis sets

PD ID	Description	ENR	SAF
INCL01A	No informed consent.	X	Х
INCL01C	ICF was not signed by subject/ parent/legal guardian; however, other family member signed on behalf the subject.	X	X

PD ID	Description	ENR	SAF
INCL02	Patients aged >= 18 was enrolled in the study.		Х
EXCL04A	Patient who has parents or legal guardians who do not give consent or allow the child to give assent.	X	Х

6 Reference

- 1. WHO Global Database on Child Growth and Malnutrition (Internet) Available from: [https://iris.who.int/bitstream/handle/10665/63750/WHO_NUT_97.4.pdf] (Accessed 11 September 2023).
- 2. COMPUTATION OF CENTILES AND Z-SCORES FOR HEIGHT-FOR-AGE, WEIGHT-FOR-AGE AND BMI-FOR-AGE (Internet) Available from: [https://cdn.who.int/media/docs/default-source/child-growth/growth-reference-5-19-years/computation.pdf] (Accessed 16 Oct 2023).

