4.1 Overall design

This trial (CLCZ696B2319E2) is a multicenter, open-label extension study for Japanese patients who have successfully completed the PANORAMA-HF OLE study (Refer to Section 1.2 Schema for study design figure). PANORAMA-HF OLE study is an on-going Phase 3b study in pediatric patients with systemic left ventricular systolic dysfunction to evaluate long- term safety and tolerability of sacubitril/valsartan in eligible PANORAMA-HF participants.

Only Japanese patients who successfully completed PANORAMA-HF OLE study and fulfill protocol requirements (see Section 5) are eligible to participate in this study, and will be offered the option to initiate treatment with sacubitril/valsartan by enrolling into this study at the discretion of the Investigator. Participants who permanently discontinued study drug treatment during PANORAMA-HF OLE study are not eligible for this study (see Section 5.2).

For all consenting patients eligibility for this study will be assessed at the first visit (Visit Day1) and the study medication will be initiated (see Section 8 for details). The first visit (Visit Day1) is the same day as the End of Study visit (Visit 599) of PANORAMA-HF OLE study. Participants who turned 18 years old during PANORAMA-HF OLE study, and who qualify, are eligible to participate in this study.

The starting dose of study drug will be determined by the Investigator considering the participant's condition The dose level at the end of study visit of PANORAMA-HF OLE study may remain the same, or the dose level may be changed at the discretion of the Investigator.

All participants have a target dose (dose level 4) of 3.1 mg/kg bid. If a participant is unable to tolerate up-titration to a higher sacubitril/valsartan dose level or at the discretion of the Investigator, participants may be maintained on lower dose levels of sacubitril/valsartan (dose level 1-3, see Table 4-1). Please see Section 6.4.1 for dose adjustments. In case of a consecutive 3-month interruption of study treatment, participant should be discontinued from the study and should complete the End of Study visit (Visit EOS).

Table 4-1 Study drug dose levels for sacubitril/valsartan

Dose levels for pediatric formulation				
Dose level 1	0.8 mg/kg bid.			
Dose level 2	1.6 mg/kg bid.			
Dose level 3	2.3 mg/kg bid.			
Dose level 4	3.1 mg/kg bid.			
Dose levels for adult formulation				
Dose level 1	50 mg bid.			
Dose level 2	100 mg bid.			
Dose level 3	150 mg bid.			

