5.1 Inclusion criteria

Participants eligible for inclusion in this study must meet all of the following criteria:

- 1. Signed informed consent as well as assent at an appropriate age must be obtained prior to participation in the study.
- 2. Male or female, inpatient or outpatient, and < 18 years of age (at the time of signing informed consent).
- 3. Patients who have completed PANORAMA-HF OLE study and are able to be safely enrolled into this study as judged by the Investigator.

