9.1 Analysis sets

The following analysis sets will be used for the statistical analyses:

- Enrolled set (ENR): All patients who signed the informed consent for the extension openlabel study.
- Safety Set (SAF): All ENR patients who received at least one dose of open-label study treatment during the extension open-label study.

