9.2 Statistical analyses

9.2.1 General considerations

- The study treatment is sacubitril/valsartan.
- The date of first administration of study treatment during this study is the day of the first non-zero dose of sacubitril/valsartan.
- The date of last administration of study treatment is the day of the last non-zero dose of sacubitril/valsartan.
- The study period starts with the date of the signature on informed consent (Visit Day 1, the same day as Visit 599 (EOS visit) of PANORAMA-HF OLE study) and ends with the date of end-of-study or premature study discontinuation visit (Visit EOS).
- The treatment period starts with the date of first administration of study treatment and ends with the date of treatment disposition. In the case that no EOS visit is undertaken (e.g., because the participant died or withdrew from the study without such a visit), the treatment period ends with the death/withdrawal date, or the last dose taken.
- In general, continuous variables will be summarized using number of observations, mean, standard deviation, median, minimum and maximum. Categorical variables will be summarized using frequencies and percentages.

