2.2 Analysis sets

The following analysis sets will be used for the statistical analyses:

- Enrolled set (ENR): All patients who signed the informed consent for the extension openlabel study.
- Safety Set (SAF): All ENR patients who received at least one dose of open-label study treatment during this extension open-label study.

The number of patients and percentage for all patients who enrolled in this study will be provided for each analysis set.

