2.7.2 Deaths

Death during the treatment period and the primary cause of death will be summarized using frequencies and percentages.

A listing of all deaths and heart transplant will also be provided.

The SAF will be used for the above analyses.

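### SAP Table 5-1 drops dosed participants aged 18 or over from the Safety Set, so their adverse events or death would be missing from every AE and death output, including the primary endpoint

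*SAP*

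**What the plan says.** Protocol 9.1 defines the Safety Set as "All ENR patients who received at least one dose of open-label study treatment during the extension open-label study". SAP 2.2 repeats this almost word for word. Neither definition has an age condition.

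SAP 5.5 then adds a deviation-based rule: "PDs excluded from the ENR or SAF are shown in Table 5-1". One row of that table, INCL02, reads "Patients aged >= 18 was enrolled in the study". It carries a mark in the SAF column and none in the Enrolled Set (ENR) column.

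On age, Protocol 4.1 states: "Participants who turned 18 years old during PANORAMA-HF OLE study, and who qualify, are eligible to participate in this study". Inclusion criterion 2 in Protocol 5.1 reads: "Male or female, inpatient or outpatient, and < 18 years of age (at the time of signing informed consent").

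SAP section 4, which is the place to record departures from the protocol's analyses, says there are none.

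**The concern.** Safety populations are normally defined by exposure, and both documents do so here. An eligibility deviation does not undo exposure, so it is no reason to remove a treated participant. Table 5-1 does this for one class of participant and so overrides the definition given in SAP 2.2.

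The study's only objective is to collect safety information, and its only endpoint is adverse events, treatment emergent or not. If a participant aged 18 or over received study drug and then had an adverse event, a serious adverse event or died, that outcome would be left out of the primary analysis and of the listings. In a study this small, the listings carry most of the information.

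The age rule itself is also unsettled. A site that relied on Protocol 4.1 could enrol and dose in good faith exactly the person whom Table 5-1 removes.

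**Working it through.** The plan has no sample size, power or precision figure to reproduce. The check is a comparison of the texts, followed by simple arithmetic on the size of the effect.

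**1. Definition against exclusion rule**

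| Source | Condition for being in the SAF |
|---|---|
| Protocol 9.1 | In ENR, at least one dose |
| SAP 2.2 | In ENR, at least one dose |
| SAP Table 5-1, INCL02 | Also not aged 18 or over when enrolled |
| SAP section 4 | No change to protocol analyses declared |

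The third row conflicts with the first two, and the fourth does not acknowledge it.

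**2. INCL02 against the other rows of Table 5-1**

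INCL01A, INCL01C and EXCL04A all concern missing or invalid consent or assent, and each removes the participant from both ENR and SAF. INCL02 is the only row that removes from the SAF alone. Since the participant stays in the ENR, consent is not the problem; the only ground is age.

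**3. Which outputs use which set**

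- SAF: primary AE analysis (SAP 2.5.2); AE and SAE tables and the listing of all AEs (2.7.1); AEs of special interest (2.7.1.1); deaths (2.7.2), including "A listing of all deaths and heart transplant will also be provided"; laboratory listing (2.7.3); vital signs (2.7.4.2); height and weight (2.7.4.3); exposure and concomitant therapy (2.4).
- SAF also: study completion, discontinuation and protocol-deviation summaries (2.3.1).
- ENR: screen-failure summaries (2.3.1). The analysis-set counts (2.2) are also given for all enrolled patients.

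No AE or death output uses the ENR. Because the deviation summary is also on the SAF, the deviation that caused the exclusion would not be counted there either.

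**4. Can the situation arise?**

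Protocol 9.2.1 dates consent to Visit Day 1, the same day as the last visit of the prior study. Someone who turned 18 during the prior study would therefore normally be 18 or over at consent and fail criterion 2. Only a person who signed before the birthday could satisfy both 4.1 and 5.1. INCL02 also leaves out the criterion's reference to the time of signing, so it might be applied even to that person.

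**5. Size**

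Inputs: maximum enrolment of 8 (Protocol 9.9.1). The number excluded, k, is not in the documents; k = 1, 2 and 3 are assumptions, and full enrolment and dosing are assumed throughout.

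- SAF size: n = 8 − k. Share lost: k/8.
- Exact two-sided 95% upper limit with zero events: 1 − 0.025^(1/n).
- Chance of seeing at least one event with an assumed true risk of 10%: 1 − 0.9^n.

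| k | n | Share lost | Upper limit, 0 events | Chance of ≥1 event at 10% risk |
|---|---|---|---|---|
| 0 | 8 | 0% | 36.9% | 57.0% |
| 1 | 7 | 12.5% | 41.0% | 52.2% |
| 2 | 6 | 25.0% | 45.9% | 46.9% |
| 3 | 5 | 37.5% | 52.2% | 41.0% |

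Two cases with k = 1:

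- The excluded participant had the only SAE: 1/8 = 12.5% (exact 95% CI 0.3% to 52.7%) becomes 0/7 = 0% (0% to 41.0%).
- The only SAE was in someone else: 1/8 = 12.5% becomes 1/7 = 14.3%.

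The reported percentage can thus move either way.

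**The case against.** Five points can fairly be made for the plan.

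- Protocol 4.1 is conditional: it covers only those who qualify, which can be read as deferring to the under-18 rule in 5.1. That stands as a reading. It leaves the sentence with almost no content, though, given when consent is signed, so the two sections still need to be reconciled.
- Eligibility is checked at Visit Day 1 and an ineligible person becomes a screen failure (Protocol 5.3 and 8.1). INCL02 matters only if someone aged 18 or over passes that check and is dosed. The documents do not say that this happened. The adult eGFR formula in Protocol Appendix 6 shows that participants aged 18 or over were expected on treatment, but that would also cover those who reach 18 after entry. This point stands, and it makes the effect conditional.
- The data are not lost altogether. AEs are still recorded in the clinical database, SAEs must still reach the sponsor within 24 hours (Protocol 8.6.3), and a gap between ENR and SAF counts would be visible. This also stands: the loss is confined to the outputs the SAP plans.
- No confidence intervals are planned, so the interval figures show scale rather than a result the study will report. Agreed.
- The exclusion was set before database lock and depends on age, not on outcome. It is therefore not outcome-driven selection. It still makes the safety summary incomplete for treated participants.

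None of these removes the conflict with the SAF definition. Even if enrolment at 18 or over is a plain deviation, the person was exposed and belongs in the SAF as both documents define it.

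**Conclusion.** The concern holds. The INCL02 mark in the SAF column contradicts the SAF definition in Protocol 9.1 and SAP 2.2 and is not declared in SAP section 4. Any consented and dosed participant it applies to would drop out of every planned AE and death output, including the study's only endpoint. At full enrolment each such participant is one eighth of the cohort, and a single serious event could be reported as none.

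The textual conflict is certain. The practical effect rests on someone aged 18 or over having been dosed, and the figures rest on all 8 places being filled. The point should be corrected whether or not such a participant exists, because the rule can hide a serious event or death from the report and costs almost nothing to remove.

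**What to change.** 1. In SAP Table 5-1, delete the SAF exclusion mark for INCL02, so that only the consent and assent rows lead to removal from the SAF. The participant then also enters the deviation summary in SAP 2.3.1, and the age deviation is reported there.
2. Reconcile Protocol 4.1 with inclusion criterion 2 in 5.1 so that a single age rule applies, and word INCL02 to match it, including the time point at which age is assessed. Which age rule applies is for the sponsor to decide.
3. If the sponsor has a reason to keep the exclusion, declare it in SAP section 4 and present the excluded participants' AEs, SAEs and deaths on the ENR.

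The cost is one cell in the SAP, to be changed before database lock, and a short protocol clarification. No new data or analyses are needed for items 1 and 2.
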